4 DATA ANALYSIS CONSIDERATIONS

4.1 Statistical Methods

The final analysis for the study will comprise descriptive analyses of cross-sectional survey data linked to baseline claims data and multivariable modeling of the primary study outcome. Analyses will be conducted using the SAS statistical software package. Illustrative table shells and figures showing the format for the analysis results will be provided separately and will include specific statistical tests that will be undertaken in support of each study objective.

4.2 Data Editing and Missing Data

Data management activities will comply with all applicable regulatory requirements and established practices for collection and validation of data and preparation of a reliable database for statistical analysis. The project specific procedures will encompass all of the data management activities associated with the implementation of the study observational plan.

The scores for each validated survey measure (i.e., mMRC, CAT) will be calculated according to the individual scoring instructions provided by the license holders. For the mMRC, a missing value is assigned if none of the five response options is selected by the patient. A CAT total score will be calculated if 2 or fewer items are missing. If 1 or 2 items are missing, the missing items will be set to the average of the non-missing items. If more than 2 items are missing, the CAT total score will be set to missing.^{xii}

Scoring instructions for all survey measures will be described in the SAP. Additionally, the specifications for a survey to be considered complete (vs. partially complete or incomplete) will be defined in the SAP. Key elements for survey completion will include responses to the mMRC and CAT, in addition to confirmation of COPD diagnosis and treatment. Additional key measures may be identified. Responses that are invalid or out of range will be considered missing. Respondents who have completed a survey that is missing a few non-key items will be included in the study analysis, but will be removed from analysis of the specific measures for which they have missing data. Removing patients from specific analyses will change the available sample size for certain measures. Because the available N may change, the valid N associated with each study measure will be reported. Select demographic claims data (e.g., age, gender) may supplement missing self-report information where possible in order to maintain sample size. Because this is a one-time, cross-sectional survey, loss of participants during subsequent observations will not be an issue.

4.3 Descriptive Analyses of Survey and Claims Data

Administrative Claims Data

Health service utilization and costs for the baseline period will be identified and presented descriptively for all-cause and COPD-related total HCRU and costs. For dichotomous variables, N (%) will be presented. For continuous variables, means, standard deviations, medians, ranges, and percentiles will be presented as appropriate. Costs will be defined as costs to the health plan and estimated costs paid by Medicare; costs will not include costs to the patient (copays, deductibles). Detailed descriptions of cost and utilization measures are provided in 3.3.2.2.

Survey Data

All study variables will be analyzed descriptively. Numbers and percents will be provided for dichotomous and polychotomous variables. Relevant measures of centrality such as means and medians will be presented for continuous measures, as well as variance measures such as standard deviations and percentiles (e.g., p25, p75). Comparisons of demographic characteristics and outcome measures will be provided. Appropriate tests (e.g., t-test, Mann Whitney-U test, chi-square test) will be used based on the distribution of the measure. For example, a one sample t-test could be used to show difference from the sample mean on a given PRO (such as CAT score) as compared to an expected value (such as CAT scores among older adults from the published literature). Pearson correlation coefficients are utilized for bivariate comparisons of CAT total score and mMRC score with selected clinical and sociodemographic characteristics.

In addition to descriptive analyses of all survey variables, survey responders and non-responders will be compared on select demographic characteristics in order to assess the generalizability of the evaluable survey sample.

Primary Objective

In order to fulfill the primary objective, the proportion of patients with low and high symptom severity will be identified based on responses to the mMRC and CAT measures. Patients may be categorized into multiple levels of severity based on the distribution of responses to one or both measures (e.g., patients with a high degree of dyspnea per the mMRC score and severe symptom burden per the CAT score may be categorized as most severe for relevant analyses).

Classification of symptom burden is based on established cutpoints for validated instruments. For the mMRC, scores ≥ 2 reflect high levels of dyspnea, and CAT scores >10 reflect high levels of COPD burden, with a 5-point difference between stable and exacerbating patients established during instrument validation^{xiii}. Correlation between these measures of symptom burden will be compared descriptively using t-tests.

Secondary Objectives

One secondary objective is to describe baseline all-cause, COPD-related, and exacerbation-related health care resource utilization, costs, and clinical characteristics. Using cross-tabulations and chi-square tests, we will describe characteristics of patients with high and low utilization and costs in terms of their symptom burden (e.g., mMRC and CAT scores), clinical characteristics (e.g., time since COPD diagnosis, treatment, comorbidity score, smoking history), and demographic and sociodemographic characteristics (age, gender, race, ethnicity, marital status, educational attainment, area of residence, and income level). Utilization and cost levels may be based on the distribution of scores among the survey sample and/or relevant literature.

The additional secondary objective is to describe patient GOLD classification. The proportion of patients in each GOLD category of combined symptom burden and exacerbation risk will be presented by treatment cohort. The calculation will use count of COPD exacerbations during the baseline combined with CAT total score and mMRC score to create mutually exclusive counts for each category (A, B, C, D)(see Section 10, Appendix 3).

Sensitivity Analysis

To assess whether differences are observed in patients based on their history of COPD exacerbations, sensitivity analysis will be conducted. This analysis will describe patient-reported symptom burden, demographic and sociodemographic characteristics, and baseline clinical characteristics for patients with and without claims-based evidence of exacerbations during the 12-month baseline period.

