3 RESEARCH METHODOLOGY

3.1 Study Design

This is a cross-sectional observational survey study of adult Medicare Advantage enrollees with evidence of COPD diagnosis and treatment. Cross-sectional survey data will be linked with retrospective claims data for the 12-month period (baseline) prior to the survey. An image illustrating the study process is provided in the Appendix.

¹¹ Celli BR, Decramer M, Wedzicha JA, et al. An Official American Thoracic Society/European Respiratory Society Statement: Research Questions in Chronic Obstructive Pulmonary Disease. *Am J Respir Crit Care Med.* 2015;191:e4-e27.

The study will use a health plan recruitment strategy. Use of this strategy requires that the health plan affiliated with Optum approve the study concept. Optum will also work with a central institutional review board (IRB) to obtain appropriate approvals for the study.

Study subjects will be identified using enrollment, medical, and pharmacy records from Optum's proprietary research claims database (ORD). A target population of 2,700 potential study participants will be contacted directly by mail. Patients will be asked to return the study survey if they consent to participate. The survey will collect information on patients' COPD duration, current treatment, symptoms, burden of illness, smoking history, and demographic and sociodemographic characteristics. Based on informal testing of the study instrument, the estimated time for survey completion is 10 minutes. Based on previous cross-sectional patient survey studies conducted by Optum, an overall response rate of 30-35% is expected.¹²

Following completion of data collection, results of the survey will be merged with claims data covering the 12-month baseline period for analysis. Pharmacy and medical claims data will be used to calculate all-cause and COPD-related health care utilization and costs, treatment patterns, and baseline clinical characteristics. Descriptive, IPTW, and multivariable statistical methodologies will be used.

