3.1.5 Study Period

An illustrative example of the study period is provided in Figure 1, which includes the sample identification, claims observation, and data collection periods described below. The 12-month period used for claims sample identification corresponds to the 12-month baseline claims analysis period for each sample.

Study period dates are estimated based on the current timeline for sample identification; changes in timelines for study tasks prior to sample identification will have a corresponding impact on the timing of later tasks.

Sample Identification Period

The sampling frame of COPD patients will be identified in Optum's research database using administrative claims data from the most recently available 12-month period at the time of sample identification, defined as the *claims sample identification period*. This period is estimated to begin 01 Jun 2017 and end 31 May 2018 for Wave 1 survey administration. This will ensure that the study sample is identified based on the most recently available pharmacy data in Optum's research database at the estimated time of identification (estimated as mid-June for Wave 1).

Medical claims for the full 12-month period will be accessed for sample identification; however, only a portion of those are complete, fully adjudicated claims. However, due to the approximate 6-month medical claims lag and 6-week pharmacy claims lag, fully complete medical and pharmacy claims data during this time period will not be available for all patients at the time of sample identification. An estimated 6 months of complete, fully adjudicated medical claims data will be available at the time of identification (01 June 2017 to 30 November 2017), with partially adjudicated claims available for the

latter 6 months of the sample identification period (01 December 2017 – 31 May 2018). Following completion of the claims lag, fully adjudicated medical claims will be accessed for the Claims Observation Period as described below. The sample identification period and the claims observation period will cover the same 12-month period for each wave of the survey.

Claims Observation Period

The baseline claims observation period will be the 12-month period closest to and prior to sample identification. The observation period for Wave 1 is estimated to be 01Jun2017-31May2018.

[figure not shown]

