3.5 Sample Size / Power Calculations

The sample size required for the study is based on several requirements. First, the study's primary outcome measures will be proportions (e.g., the proportion of patients experiencing symptoms who report low versus high symptom severity as measured by the mMRC and CAT total score). The estimated sample size is determined by the value and desired precision of the measured proportions.

Figure 6 displays the sample sizes required for various proportions, assuming a 95% confidence interval and a precision of ± 0.05 . Because the actual population proportions (e.g., the proportion of patients in each treatment cohort with mMRC scores ≥ 2 and the proportion of patients in each treatment cohort with CAT total scores ≥ 10) are unknown, the largest sample size indicated with that precision was selected. This largest value is for a proportion of 0.5 and assures a 95% confidence interval of ± 0.05 or

better for all proportions observed. Thus, a sample size of 385 completed patient surveys per treatment cohort was selected.

Figure 6 – Sample Sizes Required for Various Proportions

95% Confidence Interval	Proportion								
	0.9	0.8	0.7	0.6	0.5	0.4	0.3	0.2	0.1
±0.05	139	246	323	369	385	369	323	246	139

Since the proportion of patients experiencing symptoms will be determined from the survey and a variety of exclusion criteria can be applied only after data collection, a sampling frame of 2,700 patients is needed for an estimated evaluable sample size of 385 patients per treatment cohort. The sampling frame will be comprised of equal proportions per medication cohort (n=1,350 per cohort); however, proportional response rate by treatment cohort cannot be guaranteed. Based on the feasibility counts, Optum estimates that two waves of sample identification and survey data collection will be required to meet the target sample size. Sample identification for wave 2 will occur as soon as sufficient sample is available, which is estimated to be the month following wave 1 sample identification. The availability of the second wave will be assessed during protocol development.

Figure 7 – Estimated Final Evaluable Sample Size

Sampling frame per treatment cohort	n=1,350
Estimated response rate (30-35%)	405-470
Exclusion criteria applied following claims lag (2-5% ineligible)	8-24
Estimated final evaluable sample size per treatment cohort	385-446
Estimated total final evaluable sample size	770-892

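### With 65–70% non-response expected, responders are compared with non-responders only on demographics, so response related to claims-visible COPD severity, overall or by cohort, goes unexamined

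*Combined protocol and SAP*

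**What the plan says.** - **Response.** Section 3.1 states that "an overall response rate of 30-35% is expected". Section 3.5 sets a frame of 1,350 per cohort and adds that "proportional response rate by treatment cohort cannot be guaranteed". No analysis follows from that remark.
- **The check.** Section 4.3 (Survey Data) says "survey responders and non-responders will be compared on select demographic characteristics in order to assess the generalizability of the evaluable survey sample". It names no clinical, exacerbation, utilization or medication measure and is silent on cohort. No other section adds response weights or a sensitivity analysis for non-response.
- **Data on non-responders.** Section 3.1.5 says "Medical claims for the full 12-month period will be accessed for sample identification". It also says that only about 6 of the 12 months will be fully adjudicated by then. The complete extraction after the claims lag (sections 3.1.5 and 3.1.6) is planned for survey respondents.
- **Weighting.** Section 4.4 weights by the probability of treatment. The Appendix 4 covariates include exacerbation count, Quan-Charlson score, COPD-related fills and ambulatory visits, together with survey items such as general health and pack years.
- **What is reported.** Section 3.4.1 makes the proportions with CAT ≥10 and mMRC 2–4 primary endpoints, overall and by cohort.
- **Limitations.** Section 5 mentions sampling, coverage and measurement error, but not response related to severity.

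**The concern.** Demographic similarity says little about whether sicker or less sick patients return the questionnaire. If response depends on COPD severity, the reported proportions with high symptom burden are shifted away from those of the invited population. If the dependence also differs between cohorts, the unweighted cohort contrast is shifted too. Equal response rates in the two cohorts would not reveal either problem. Claims measures of severity exist at identification for everyone invited, so part of this could be examined, and the plan does not do so.

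**Working it through.** **1. The plan's own figures.** Section 3.5 works from a 95% interval of ±0.05 at a proportion of 0.5: n = 1.96² × 0.5 × 0.5 / 0.05² = 384.1, rounded up to 385. That agrees with the plan. For Figure 7, 1,350 × 0.30 × 0.95 = 384.75 (stated 385). At the upper end 470 − 24 = 446, as stated; unrounded, 1,350 × 0.35 × 0.95 = 448.9.

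**2. Non-response.** 2,700 × (1 − 0.35) = 1,755 and 2,700 × (1 − 0.30) = 1,890, or about 878–945 per cohort.

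**3. Possible unweighted bias (illustration).** The documents give no response rates by severity, so all rates here are assumed. With true proportion p, and response rH among high-burden and rL among low-burden patients, the observed proportion is p·rH / (p·rH + (1 − p)·rL). Take p = 0.65 in both cohorts, with one cohort responding at 32% regardless of symptoms.

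- Other cohort 30% if high, 36% if low (32.1% overall): 0.195 / (0.195 + 0.126) = 60.7%, a false difference of 4.3 points.
- Other cohort 28% and 40% (32.2% overall): 0.182 / (0.182 + 0.140) = 56.5%, a false difference of 8.5 points.
- The same pattern in both cohorts: no false difference, but a level shift. For example, p = 0.50 with 36% and 24% gives 0.18 / (0.18 + 0.12) = 60%.

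These figures are unweighted and let response depend directly on symptoms.

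**4. What IPTW does and leaves (assumed example).** A claims severity marker is present in 50% of each cohort. High burden is 80% with the marker and 50% without, so 65.0% overall. Per 100 invited, cohort A responds at 32% throughout (16 with the marker, 16 without). Cohort B responds at 26% with the marker and 38% without (13 and 19).

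| Analysis | A | B |
|---|---|---|
| Crude | 65.0% | (13 × 0.8 + 19 × 0.5)/32 = 62.2% |
| IPTW among responders (marker 29/64 in both) | 63.6% | 63.6% |
| Weighted by 1/response within cohort (marker 50% in both) | 65.0% | 65.0% |

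IPTW removes the 2.8-point false difference. It leaves both proportions 65.0 − 63.6 = 1.4 points low. Response weighting restores the level, because here response depends only on the marker.

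**5. Combining the two weights.** If the response model is fitted within cohort, the treatment model has to be refitted on the response-weighted respondents. Multiplying the responders-only IPTW weight by the cohort-specific inverse response probability gives B total weights in proportion to 29/0.26 = 111.5 with the marker and 35/0.38 = 92.1 without. B becomes (111.5 × 0.8 + 92.1 × 0.5)/203.6 = 66.4% against 63.6% in A, which brings back a false 2.8 points. With the treatment model refitted, both are 65.0%.

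**6. Can the added check see anything?** At 30% response there are 405 responders and 945 non-responders per cohort. For a claims indicator with assumed prevalence 20–50%, 80% power (two-sided 0.05) is reached at a difference of about 7–8 points within a cohort. Pooled (810 v 1,890) it is about 5–6 points.

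**The case against.** The strongest reply is that planned IPTW already covers most of what claims could correct in the cohort contrast. Exacerbation count, Quan-Charlson score, COPD-related fills and ambulatory visits are all in Appendix 4, and step 4 shows the false difference going to zero. That stands. A reader might infer that IPTW does nothing about non-response; the documents do not support that. What IPTW leaves is the shifted level of the proportions, and it gives no information on who failed to respond.

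A reader might also take the 4.3 and 8.5 points as the bias in the planned primary comparison, or as what the fix would remove. They are neither. So far as claims capture the severity behind response, IPTW already acts on it. So far as they do not, neither a claims comparison nor response weights can reach it. Bias in the contrast also needs response that depends on severity differently in the two cohorts. Both have the same criteria, mailing process and materials, and nothing in the documents shows such a difference. The remark in section 3.5 concerns response rates, not severity.

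Two further inferences go too far. Section 4.3 does not say that the comparison is pooled; it is silent on cohort, and section 4.1 leaves table shells and specific tests to a separate document. Nor are complete severity data already held for non-responders. Appendix 2 identifies exacerbations after the claims lag, and the incomplete 6 months are those containing the qualifying fill. The identification-date data are still usable if both groups are measured at that same date.

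**Conclusion.** The point holds in a limited form. With 65–70% non-response, the planned check cannot show whether response is related to claims-visible COPD severity, in either cohort or differently between them. The planned IPTW protects much of the cohort contrast on the measured covariates. It does not protect the overall and per-cohort proportions, which are primary endpoints.

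The size cannot be estimated from the documents. In the assumed example the level shift after IPTW is 1.4 points; the 4.3 and 8.5 points show only what unweighted bias could be under assumed response rates. The example assumes that response depends on symptoms only through a measured marker. Response that depends on CAT or mMRC beyond claims measures remains unobservable and belongs in the limitations. The change is worth making, but nothing here shows the primary comparison to be invalid.

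**What to change.** 1. In section 4.3, compare responders and non-responders within each cohort, using standardized differences, on exacerbation count, Quan-Charlson score, COPD-related fills, ambulatory visits and days since first fill. Take these from the same identification-date pull for both groups, and state whether responders are counted before or after the post-survey exclusions.
2. Add one sensitivity analysis weighting respondents by the inverse probability of response, modelled within cohort from these measures. Report the overall and per-cohort proportions with this weight. For the cohort contrast, multiply it by a treatment weight refitted on the response-weighted respondents.
3. Name severity-related non-response in section 5, including the part that claims cannot show.

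**Cost.** A little more programming, and slightly wider intervals in the weighted sensitivity analysis. Medical claims for the last 6 months are only partly adjudicated unless non-responders' claims are re-extracted after the lag. The sponsor should confirm that IRB and health-plan approvals cover this use of non-responders' claims. No change to sample size or fielding is needed.

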
	
count of COPD exacerbations combined with CAT total score and mMRC score. GOLD categories are mutually exclusive. Results will be presented overall and by treatment cohort (FLUT/SAL or UMEC/VI).
 
Multivariable modeling of the primary objective will be conducted following review of descriptive and IPTW results. Each model will examine the relationship between symptom burden and treatment with FLUT/SAL or UMEC/VI. The dependent variable for the models will be CAT total score and mMRC score, respectively; covariates for the models will be based on clinical and analytic significance.

Sample Size and Power
	
The study sample is estimated to include 385 patients per cohort with evidence of COPD diagnosis and single-inhaler dual therapy treatment with FLUT/SAL or UMEC/VI. A sample size of n=385 per cohort is required to assess statistical significance with a 95% confidence interval at ± 0.05 with 80% power. A sampling frame of 2,700 patients is estimated to be used to reach the target evaluable sample size, n=770 patients (385/cohort). Based on patient counts and response rate estimates, it is anticipated that two waves of data collection will be needed to meet the target sample size.
 
This estimated study sample size is sufficient to detect proportional differences in PRO outcomes between two cohorts of patients (i.e., patients treated with FLUT/SAL or UMEC/VI who have severe symptoms as measured by a CAT total score ≥ 10 or an mMRC score ≥ 2); other stratifications tied to primary and secondary endpoints may be considered for statistically powered analyses as sample size allows.

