3.4.1 Primary Endpoint

- **Patient-reported symptom burden.** Scores will be presented from validated instruments measuring dyspnea (mMRC) and condition-related burden of illness (CAT). Mean total, summary, and/or domain scores and standard deviations will be presented for each scale/item (as described in Section 3.3.1.3). The proportion of patients with high and low symptom burden on both PRO measures will be calculated. Results will be presented for the overall study sample and by treatment cohort (FLUT/SAL or UMEC/VI).
- **Proportion of patients reporting COPD symptoms while treated with FLUT/SAL or UMEC/VI.** The proportion of patients who report COPD symptoms will be computed for survey respondents. Two calculations will be presented: the number of COPD patients who report COPD symptoms as measured by a CAT total score ≥ 10 , divided by the total number of respondents with a CAT total score; and the number of COPD patients with an mMRC score of 2-4, divided by the total number of respondents with an mMRC score. Results will be presented for the overall study sample and by treatment cohort.
- The mMRC and CAT instruments are included to correspond with current GOLD guidelines.

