3.4.2 Secondary Endpoint(s)

- **Baseline health care resource utilization and costs.** All-cause and COPD-related health care costs will be presented for the 12-month baseline period. Mean, median, and standard deviations will be presented for total costs and utilization and for each category of costs (i.e., pharmacy + medical, and the subcategories of medical costs as described in Section 3.3.2.2). Costs and counts will be presented overall and for the subset of patients utilizing the selected type of service. The proportion of patients receiving services for each type of service and the proportion of patients with non-zero costs for each type of cost will be calculated. Results will be presented for the overall study sample and may be stratified by relevant subgroups for analysis (e.g., by low versus symptom burden as measured by patient mMRC and CAT scores).
- **Patient clinical characteristics.** The proportion of patients with evidence of selected clinical characteristics will be presented. The top 20 claims-based comorbidities and up to 10 COPD-related comorbidities will be identified. The percent of patients with each condition will be identified. Mean and standard deviation will be calculated for the Quan-Charlson comorbidity score. Results will be presented for the overall study sample and may be stratified by relevant subgroups for analysis (e.g., by low versus high symptom burden as measured by patient mMRC and CAT scores).
- **Patient GOLD classification.** The proportion of patients in each GOLD category of symptom burden and exacerbation will be presented. The calculation will use count of COPD exacerbations during the baseline combined with CAT total score and mMRC score to create mutually exclusive counts for each category (A, B, C, D) (Section 10, Appendix 3).

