Depending on the distribution of the measure, the CAT and mMRC outcomes may be analyzed as a continuous or dichotomous measure. In general, continuous variables are analyzed using ordinary least square regression models. If transformed into a dichotomous measure (e.g., patients with a CAT total score > 10 or an mMRC score ≥ 2), the probability of an event will be modeled using logistic regression. Logistic regression models fit a maximum-likelihood logit model. Following standard procedure, regression diagnostics will be performed for each model to assess goodness of fit and violations of model assumptions (e.g., multicollinearity, heteroskedasticity). When there are violations of the model, they will be noted and appropriate corrections made to the data (i.e., typically through transformation of either the independent or dependent variables) or in the method of estimation. In addition, the fitted and the observed data will be examined to uncover outliers, their effect on the analysis, and possible misspecification of the initial equation.

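### The CAT cut-off for high symptom burden is ≥10 in the primary endpoint and sample-size texts but >10 in the Section 4.3 classification rule and the Section 4.5 example

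*Combined protocol and SAP*

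**What the plan says.** Five places in the protocol state a CAT threshold.

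| Place | CAT threshold | Wording |
|---|---|---|
| Synopsis, Sample Size and Power | ≥10 | "severe symptoms as measured by a CAT total score ≥ 10" |
| Section 3.4.1, Primary Endpoint | ≥10 | "who report COPD symptoms as measured by a CAT total score ≥ 10" |
| Section 3.5, Sample Size / Power Calculations | ≥10 | "the proportion of patients in each treatment cohort with CAT total scores ≥ 10" |
| Section 4.3, Primary Objective | >10 | "CAT scores >10 reflect high levels of COPD burden" |
| Section 4.5, Multivariable Analysis | >10 | "If transformed into a dichotomous measure (e.g., patients with a CAT total score > 10" |

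The mMRC threshold is the same wherever it appears (≥2, or equivalently 2–4).

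Section 3.4.1 also makes the low/high split a primary output: "The proportion of patients with high and low symptom burden on both PRO measures will be calculated". It attaches no cut-off to that sentence. Section 4.3 says that, for the primary objective, "the proportion of patients with low and high symptom severity will be identified based on responses to the mMRC and CAT measures", and then gives the >10 rule. Section 3.4.2 allows secondary endpoints to be stratified "by low versus high symptom burden as measured by patient mMRC and CAT scores", again without a cut-off.

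**The concern.** The two thresholds differ only for a CAT total of exactly 10, but that score lies on the boundary of a primary proportion. The proportion reporting symptoms is fixed at ≥10 by Section 3.4.1. The low/high burden proportion, also primary, takes its only explicit classification rule from Section 4.3, which is >10. If each section is programmed as written, the same report carries two primary percentages that appear to describe the same split and disagree.

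Two further uses inherit the ambiguity: the optional low/high strata for the secondary endpoints, and a logistic model for CAT if the outcome is dichotomised. That model could then be fitted to a different outcome from the endpoint it is meant to support. Section 4.5 leaves the choice between continuous and dichotomous analysis to the observed distribution and settles final model outcomes after descriptive results are seen. An unsettled threshold adds one more choice that could be made after seeing the data.

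**Working it through.** **Are these two different constructs?** One reading is that ≥10 means having symptoms and >10 means high burden. The protocol does not keep them apart. Section 3.5 gives low versus high severity on mMRC and CAT as its example of the primary proportions, then names those proportions with CAT ≥10. The synopsis attaches ≥10 to severe symptoms. Section 4.3 presents its rule as an established cut-point and does not say that a second threshold is intended. The split is the same one.

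**Is it a reading error from the PDF?** Unlikely. In both Section 4.3 and Section 4.5, the sentence that prints > for CAT prints ≥ for mMRC.

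**Sample size.** Section 3.5 uses a 95% interval, half-width 0.05 and p = 0.5:

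n = 1.96² × 0.5 × 0.5 / 0.05² = 384.2, rounded up to 385.

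This reproduces the stated figure. Because it takes the worst case p = 0.5, it does not depend on the cut-off.

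**Who changes group.** The CAT has eight items scored 0–5. Section 4.2 replaces one or two missing items by the mean of the rest, so a prorated total is 8s/7 or 8s/6 for an integer sum s.
- One item missing: the nearest totals are 8×8/7 = 9.14 and 8×9/7 = 10.29.
- Two items missing: they are 8×7/6 = 9.33 and 8×8/6 = 10.67.

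None equals 10, so only respondents with all eight items and a total of exactly 10 change group. The exception would be if prorated totals were rounded, on which Section 4.2 is silent.

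**Size of the shift in each proportion.** Proportion at ≥10 minus proportion at >10 = P(CAT = 10). The protocol gives no CAT mean or SD, so the following is an assumption: a normal distribution discretised to the integers 0–40 and renormalised.

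| Mean, SD | P(CAT = 10) | Patients of 385 | ≥10 | >10 |
|---|---|---|---|---|
| 12, 7 | 5.7% | 21.9 | 66.4% | 60.7% |
| 15, 8 | 4.2% | 16.2 | 77.4% | 73.2% |
| 18, 8 | 3.1% | 11.8 | 86.5% | 83.4% |
| 20, 7 | 2.1% | 7.9 | 93.5% | 91.4% |

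For scale, the 95% half-width at 77.4% with n = 385 is 1.96 × √(0.774 × 0.226 / 385) = 4.2 points. In that scenario the definitional shift is as large as the sampling margin.

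**Between-cohort difference.** With means 15 and 17 and SD 8, the expected difference is 6.3 points at ≥10 and 7.1 points at >10, a shift of 0.76 before rounding. Over mean pairs 12/14, 15/16, 15/17 and 18/20 with SD 7, 8 and 9, the expected shift is 0.29–0.99 points. These are expectations, not bounds. In 300,000 simulated samples of 385 per cohort (15 versus 17, SD 8), the 95% range of the shift was −1.8 to +3.4 points. An unadjusted chi-square test at 0.05 was significant under one cut-off and not the other in 14.6% of samples. With both means at 15, the range was −2.9 to +2.9 points and the result differed in about 4% of samples.

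**The case against.** The strongest reply is that this is a slip with an obvious resolution. The endpoint definition and both sample-size texts say ≥10, and a programmer would probably follow the endpoint. Section 4.1 says table shells are provided separately, and Section 4.2 defers scoring instructions to the SAP, so no conflicting table can actually be seen. Section 4.5 offers >10 only as an example inside a conditional. The planned model outcome and hypothesis 1A concern the CAT total score, and the treatment comparison is to be weighted and modelled, not a bare chi-square test. The 15% figure depends on an assumed 2-point true difference, which puts the test at intermediate power (about 60% at ≥10 and 64% at >10), where such disagreement is naturally common.

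Most of this stands as a limit on the consequence. The conflicting tables follow from applying each section as written and have not been observed. The simulation is an illustration under assumed distributions, and its chi-square result does not carry over to the weighted analysis. It does not remove the contradiction. Section 4.3 is the section an analyst would use to build the low/high split, and it states >10 outright as the rule. The deferrals to shells and SAP do not mark the threshold as open, and those documents would be written from a text that holds two values.

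**Conclusion.** The concern holds. The threshold for a primary proportion is stated in two incompatible ways, and no text reconciles them. What is certain is that each cohort's proportion differs between the two definitions by exactly the share of patients scoring 10. The size of that share is assumption-based: about 2–6% if scores are roughly normal with mean 12–20 and SD 7–9. The effect on the between-cohort difference is smaller in expectation, under 1 point in the scenarios tried, but can be a few points in either direction in a single sample.

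The planned 385 per cohort, hypothesis 1A on the total score and every mMRC result are unaffected. The effect on a logistic model arises only if CAT is dichotomised. The GOLD figure in Appendix 3 is not visible in the text reviewed, so no inconsistency is claimed there. This is a correction that should be made, not one that threatens the study's main analysis.

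**What to change.** Before analysis, settle on one cut-off and use it throughout:

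- Change Sections 4.3 and 4.5 to a CAT total score of ≥10, which agrees with the primary endpoint and both sample-size texts.
- Add one sentence stating that this cut-off also defines the low/high burden proportion in Section 3.4.1 and any low/high strata in Section 3.4.2.
- Check that the GOLD grouping in Appendix 3 uses the same value.

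The cost is two wording changes, one clarifying sentence and one check. Data collection, sample size and the planned models do not change.
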